7.6 Sample Handling, Storage, and Shipment

All blood samples are to be tested at a central laboratory with the exception of the safety laboratory panel which will be tested at a local laboratory (see [Appendix B](#)). The urine dip-stick for the safety laboratory, urine pregnancy tests, urine drug screening, and urine cotinine tests will be done by personnel at the study sites.

Confidentiality Statement

Data and information contained in this document are considered to constitute trade secrets and confidential commercial information, and the legal protections provided to such trade secrets and confidential information are hereby claimed under the provisions of applicable law. No part of this document may be publicly disclosed without the written consent of Philip Morris Products S.A.

Detailed procedures for collection and handling of samples are described in a separate sample handling manual (SHM). Safety laboratory samples will be destroyed as per the laboratory's standard procedures. All primary and back-up samples for the assessments of BoExp (except bio-banking samples) of discontinued subjects will be destroyed after the bioanalytical report has been finalized or the database has been locked, whichever comes last. Personnel at the facility/-ies where samples are stored will be informed in writing by the Sponsor when destruction of the samples will be allowed.

The bioanalytical lab(s) will be listed in the SHM.

7.6.1 Blood Samples

Blood samples will be collected by qualified and trained site personnel. Subjects should be in a seated position during blood collection. The maximal total volume of blood drawn for each subject will be around 180 mL, which includes about 20 mL for safety and repeated analysis, about 20 mL for long-term storage of the bio-banking samples for further analysis of biomarkers (only if additional consent is given) and 20 mL for long-term storage bio-banking samples for further analysis of transcriptomics and lipidomics (only if additional consent is given) (section 7.6.3).

The blood sampling for transcriptomics and lipidomics, and the data related to these samples will be anonymized. Anonymized data and samples are initially single or double coded where the link between the subjects' identifiers and the unique code(s) is subsequently deleted.

7.6.2 Urine Samples

Spot urine samples will be used for the urine drug screening, urine cotinine test, urine pregnancy test and safety urine analysis.

Twenty four-hour urine will be collected from Day -2 to Day 6 on site to measure BoExp. On Day 1, product use must not start prior to the end of urine collection of Day -1.

Twenty four-hour urine sample collection for Day -2 will start approx. at 06:30 AM on Day -2 after the first morning void which should be discarded and will end after 24 hours \pm 1 hour on Day -1

From Day -1 on, the 24-hour urine collection for the respective day will immediately start after the end of 24-hour urine collection of the previous day (after 24 hours \pm 1 hour) (Appendix A). After nearly 24-hours of urine collection, subjects will empty their bladder again and this urine will be used as the final portion of the 24-hour urine sample. During the collection period, all urine passed must be collected and put into the sampling container, with the exception of about 10 mL for the spot urine tests (described above). The spot urine sample of the amount of 10 mL for the urine pregnancy test and safety urine analysis will be taken from the final portion of the 24-hour urine sample before putting this final portion into the sampling container. The amount of 10 mL for the spot urine tests should not be subtracted from the 24-hour urine

Confidentiality Statement

Data and information contained in this document are considered to constitute trade secrets and confidential commercial information, and the legal protections provided to such trade secrets and confidential information are hereby claimed under the provisions of applicable law. No part of this document may be publicly disclosed without the written consent of Philip Morris Products S.A.

sample. No urine must be passed into the toilet. The start and the end time of urine collection will be recorded by the subject in a form and checked by the site collaborators. The volume of 24-hour urine will be measured by the site collaborators upon collection of urine containers from the subjects.

For assessment of urine BoExp, creatinine for normalization of urine BoExp, sample bio-banking and urine mutagenicity, aliquots from the 24-hour urine collection will be taken. In the schedule of events for the 24-hour urine collection (see [Appendix A](#)) the dot corresponds to the day on which the 24-hour urine collection period starts. For example, NEQ measured at Day 5 in the 24-hour urine collection starts on Day 5 and ends in the morning of Day 6 prior to Discharge.

For the Discharge on Day 6, subjects will empty their bladder shortly before 06:29 AM. This will be the last urine portion for the 24-hour urine for the Day 5 dot mark in the schedule of events. The spot urine sample of the amount of 10 mL for the urine pregnancy test and safety urine analysis will be taken from the final portion of the 24-hour urine sample before putting this final portion into the sampling container. The amount of 10 mL for the spot urine tests should not be subtracted from the 24-hour urine sample. For assessment of urine BoExp, creatinine, and samples for bio-banking (if consent received, 5 tubes of urine will be taken for bio-banking), aliquots from the 24-hour urine collection will be taken. In the schedule for 24-hour urine collection assessments, the dot corresponds to the day on which the 24-hour urine collection period ends.

See [Appendix A](#) for the timepoints of assessment.

7.6.3 Bio-Banking for Long-Term Storage of Blood and Urine

If a subject gives consent for sample bio-banking for long-term storage, additional samples of urine (from the 24-hour urine collection) and serum/plasma (20 mL of blood in total) will be collected as follows:

- Samples from the 24-hour urine will be collected from the urine collections that started on Day -1 and on Day 5, respectively.
- Serum/plasma will be collected on Day -1 and Day 6.

These samples are intended for possible later analysis of additional biomarkers. No genetic or transcriptogenomics testing will be performed on these samples.

If a subject gives consent for sample bio-banking of whole blood/plasma for further transcriptomics and plasma for lipidomics analysis, an additional 10 mL of blood will be collected for each assessment: 5 mL for transcriptomics will be aliquoted in 2 tubes (2.5 mL of blood/tube); for lipidomics, the 4 mL of blood will be centrifuged and the plasma aliquoted in 4 tubes of 500 µL each.

Confidentiality Statement

Data and information contained in this document are considered to constitute trade secrets and confidential commercial information, and the legal protections provided to such trade secrets and confidential information are hereby claimed under the provisions of applicable law. No part of this document may be publicly disclosed without the written consent of Philip Morris Products S.A.

The samples intended for sample bio-banking will be kept frozen and shipped to a central storage facility. After the final CSR is signed, samples of plasma/serum/blood will be stored for a maximal period of 5 years and samples of urine will be stored for a maximal period of 2 years. The blood/plasma bio-banking for transcriptomics and lipidomics will be stored for a maximum period of 5 years.

If a subject withdraws his/her consent for sample bio-banking the facility at which the samples are stored will follow their procedures for destruction of banked samples as stated in section 7.6.3.

See [Appendix A](#) for the timepoints of assessment.

7.7 Other Study Procedures

7.7.1 Human Puffing Topography Assessment

Human puffing topography involves the measurement of each smoker's unique way of smoking CCs or using CHTP 1.0 using the HPT SODIM® device. The HPT SODIM® device, model SPA/M (SODIM® Instrumentation, Fleury les Aubrais, France) is a device which is used to measure puffing topography (see [Appendix C](#)). It consists of a special sample holder (containing a constriction in the middle) which is placed between the subject's mouth and the filter of the CC or CHTP 1.0 being smoked/used. The sample holder is connected by 2 narrow tubes to a portable data logger/recording system (see [Appendix C](#) for a description of the device). Any malfunction of the HPT SODIM® portable device will be documented in appropriate log.

At Day -2, the HPT SODIM® device has to be used for all CC smoked for all subjects. On Day 1 and Day 4 of the confinement period, the HPT SODIM® device has to be used for every product use for all subjects in the CC and CHTP 1.0 arms.

Smoking topography with the HPT SODIM® device will not be recorded for subjects smoking CC that are incompatible with the HPT SODIM® device (e.g., slim CC).

For each subject, one HPT Device (configured for CC use) will be assigned at Day -2 which will be used by that subject on all HPT assessments days during baseline. Then, at Day 1, subjects randomized to the CC arm will still use the same HPT Device that was used during baseline whereas new HPT Devices (configured for CHTP 1.0 use) will be assigned for subjects randomized in the CHTP 1.0 arm.

The Sponsor will provide training on the use of the HPT SODIM® device to the site collaborators. The site collaborators will, in turn, provide training to the subjects. All HPT SODIM® devices will be returned to the Sponsor after completion of the study.

Confidentiality Statement

Data and information contained in this document are considered to constitute trade secrets and confidential commercial information, and the legal protections provided to such trade secrets and confidential information are hereby claimed under the provisions of applicable law. No part of this document may be publicly disclosed without the written consent of Philip Morris Products S.A.

7.7.2 Human Puffing Topography Parameters

The HPT SODIM® device measures and records the flow and other per-puff parameters listed in Table 4 below. From the per-puff parameters (Table 4), the per-cigarette parameters shown in Table 5 will be derived (representing average values or totals per cigarette).

Prior to calculation of the per-CHTP 1.0/CC parameters, the Sponsor's HPT group will validate the data and discard any invalid data. Only valid data for the per-CHTP/cigarette parameters will be part of the study database and will be analyzed.

Table 4 Human Puffing Topography – Per-Puff Parameters

Description	Variable	Unit
Puff number	Ni	
Puff volume	Vi	ml
Puff duration	Di	s
Average flow [Vi/Di]	Qmi	ml/s
Peak flow	Qci	ml/s
Inter puff interval	li	s
Sum of li and Di	DFi	s
Work [INT Pmi*FinalFlow*dt]	Wi	mJ
Average pressure drop	Pmi	mmWG
Peak pressure drop	Pci	mmWG
Average resistance [Pmi/Qmi]	Rmi	mmWG/ml/s
Peak resistance [Pci/Qci]	Rci	mmWG/ml/s

Table 5 Human Puffing Topography – Per-CHTP 1.0/Cigarette Parameters

Description	Variable	Formula	Unit
Total number of puffs	NPC	$\sum Ni$	
Total puff volume	TVOL	$\sum Vi$	ml
Average puff volume	AvgVi	$\sum Vi / NPC, i=1 \dots NPC$	ml
Average puff duration	AvgDi	$\sum Di / NPC, i=1 \dots NPC$	s
Total puff duration	TDi	$\sum Di$	s
Average flow	AvgQmi	$\sum Qmi / NPC, i=1 \dots NPC$	ml/s
Peak flow	AvgQci	$\sum Qci / NPC, i=1 \dots NPC$	ml/s

Confidentiality Statement

Data and information contained in this document are considered to constitute trade secrets and confidential commercial information, and the legal protections provided to such trade secrets and confidential information are hereby claimed under the provisions of applicable law. No part of this document may be publicly disclosed without the written consent of Philip Morris Products S.A.

Description	Variable	Formula	Unit
Total inter puff interval	Tli	$\sum li$	s
Average inter puff interval	Avgli	$\sum Qci / NPC, i=1 \dots NPC$	s
Total smoking duration	TDFi	$\sum DFi$	s
Total work	TWi	$\sum Wi$	mJ
Average work	AvgWi	$\sum Wi / NPC, i=1 \dots NPC$	mJ
Average pressure drop	AvgPmi	$\sum Pmi / NPC, i=1 \dots NPC$	mmWg
Average peak pressure drop	AvgPci	$\sum Pci / NPC, i=1 \dots NPC$	mmWg
Puffing intensity	SMINT	TVOL/TDFi	ml/s
Puffing time index	PTI	$(100*TDi)/TDFi$	%
Puff frequency	PFeq	$NPC/(TDFi/60)$	Min ⁻¹

7.7.3 CHTP Plug and Diffuser Analysis

All CHTPs 1.0 used on Day 4 will be collected and sent to an external laboratory for analysis of smoke nicotine in the plug and diffuser.

7.7.4 Handling and Collection of CHTPs 1.0 after use on Day 4

- Right after the end of using a CHTP 1.0 on Day 4, the used CHTP 1.0 will be inserted into the glass tube provided with the heat source oriented to the bottom of the glass tube. The extinguisher must not be used beforehand.
- The glass tube is then placed in the glass tube holder to let CHTP 1.0 used cooling down.
- Within 12 hours after the CHTP 1.0 collection, the combi filter will be manually separated from the rest of CHTP 1.0 by applying an appropriate bending force (between the diffuser and the polymer-film filter [PLA] section).
- Close the tube with a yellow cap and store the tubes at $4 \pm 3^{\circ}\text{C}$ until shipment.

Further details will be provided in the site manual.

7.8 Questionnaires

The subject questionnaires and the cough-VAS used in this study will be answered and assessed by the subject directly on paper copy. All subject-reported outcome data as well as instructions will be provided in the subject's local language. The questionnaires and the cough-VAS will be viewed for completeness by the site collaborators and subjects will be requested to complete any missing information.

Confidentiality Statement

Data and information contained in this document are considered to constitute trade secrets and confidential commercial information, and the legal protections provided to such trade secrets and confidential information are hereby claimed under the provisions of applicable law. No part of this document may be publicly disclosed without the written consent of Philip Morris Products S.A.

Symptoms or worsening of symptoms documented on any of the questionnaires or on the VAS do not need to be documented as additional AEs because the questionnaires and the cough-VAS will be analyzed as part of the final report. However, it is at the discretion of the Investigator or designee to decide whether to document such symptoms as additional AEs. The main source for AE collection will be the face-to-face interview between the subject and the site collaborators, using open, non-directive questions (section 8).

See [Appendix A](#) for the timepoints of assessment.

The questionnaires should be done at the same time for each visit.

7.8.1 Fagerström Test for Nicotine Dependence (Revised Version)

Potential nicotine dependence will be assessed via a subject self-reported questionnaire using the Fagerström test for nicotine dependence (FTND) in its revised version [17].

The questionnaire consists of six questions which will be answered by the subject himself/herself. The scores obtained on the test allow the classification of nicotine dependence in three different levels: mild (0-3 points), moderate (4-6 points), and severe (7-10 points).

See [Appendix A](#) for the timepoints of assessment.

7.8.2 Assessment of Cough-VAS

Subjects will be asked to self-report and to assess the respiratory symptom ‘cough’ on a VAS, on three Likert scales, and with an open question. Assessment of cough will be conducted irrespective of the time.

Subjects will be asked if they have experienced a regular need to cough, e.g., whether they have coughed several times in the previous 24 hours prior to assessment. If the answer is ‘yes’, subjects will be asked to complete a VAS, 3 Likert scales and to answer the open question.

On the VAS, subjects will assess how bothersome their cough was during the previous 24 hours. The VAS ranges from ‘not bothering me at all’ to ‘extremely bothersome.’

Furthermore, subjects will assess the intensity and frequency of cough and the amount of sputum production during the previous 24 hours on Likert scales.

The intensity of cough will be assessed on a 5-point Likert scale ranging from 1 to 5, with 1 = very mild – 2 = mild – 3 = moderate – 4 = severe – 5 = very severe.

The frequency of cough will be assessed on a 5-point Likert scale ranging from 1 to 5, with 1 = rarely – 2 = sometimes – 3 = fairly often – 4 = often – 5 = almost always.

The amount of sputum production will be assessed on a 4-point Likert scale ranging from 0 to 3, with 0 = no sputum – 1 = a moderate amount of sputum – 2 = a larger amount of sputum – 3 = a very large amount of sputum.

Confidentiality Statement

Data and information contained in this document are considered to constitute trade secrets and confidential commercial information, and the legal protections provided to such trade secrets and confidential information are hereby claimed under the provisions of applicable law. No part of this document may be publicly disclosed without the written consent of Philip Morris Products S.A.

Finally, subjects will be asked to share any other important observations with the site collaborators about their coughing.

See [Appendix A](#) for the timepoints of assessment.

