7 STUDY PROCEDURES

Personnel performing or recording study assessments must have appropriate and fully documented training. Quality control (QC) measures have to be in place. An overview of all study assessments is shown in the schedule of events ([Appendix A](#)). Considering that not all subjects can have a procedure at the same time point, adequate time windows will be given for each study procedure and each time point in section 9. Site personnel will adhere to the site's standard operating procedures (SOPs) for all activities or otherwise specified by the protocol. Appropriate medical advice will be provided to the subject in case of any medical findings requiring health care.

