Data and information contained in this document are considered to constitute trade secrets and confidential commercial information, and the legal protections provided to such trade secrets and confidential information are hereby claimed under the provisions of applicable law. No part of this document may be publicly disclosed without the written consent of Philip Morris Products S.A.

Abbreviations: AE = Adverse event; CC = Conventional cigarette(s); CO = Carbon monoxide; COHb = Carboxyhemoglobin; QSU–brief = Questionnaire of smoking urges (brief version); MCEQ = Modified cigarette evaluation questionnaire; SAE = Serious adverse event.

Table 9 Time Schedule – Day -1

Time	Blood Sample	Procedures	Additional Information
Start of Procedure		Baseline Period (Day -1)	
6:30 AM		Start of smoking	
		AE/SAE recording	At any time of the day
		Concomitant medications	At any time of the day
		End of 24-hour urine sample collection for Day -2	The urine is collected for 24 hours \pm 1 hour. The end of the 24-hour urine collection should be prior to smoking the first CC.
		Start of 24-hour urine sample collection for Day -1.	The start of 24-hour urine collection of Day -1 should be subsequent to the end of 24-hour urine collection of Day -2
		Urine sample to be taken from the 24-hour urine of Day -2.	Aliquots from 24-hour urine will be collected according to Table A2 .
Prior to 11:30 AM	√	CYP2A6 activity in plasma	Has to be done early in the morning prior smoking
Prior to 11:30 AM		Vital signs (blood pressure, pulse rate, respiratory rate)	At least 5 minutes in supine position
Prior to 11:30 AM		MNWS questionnaire	Has to be done prior to smoking
Prior to 11:30 AM		Assessment of cough (VAS)	Has to be done prior to smoking

Confidentiality Statement

Data and information contained in this document are considered to constitute trade secrets and confidential commercial information, and the legal protections provided to such trade secrets and confidential information are hereby claimed under the provisions of applicable law. No part of this document may be publicly disclosed without the written consent of Philip Morris Products S.A.

Time	Blood Sample	Procedures	Additional Information
Start of Procedure		Baseline Period (Day -1)	

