9.2.3 Exposure Period (Days 1 to 5)

Table 10 shows the assessments that will be performed on Day 1.

The collection of 24-hour urine of Day -1 starting on Day -1 will end on Day 1.

The collection of 24-hour urine sample for Day 1 will start on Day 1 and will end on Day 2.

Table 10 Time Schedule – Day 1

Time	Blood Sample	Procedures	Additional Information
Start of Procedure		Day 1	
6:30 AM		Start of use of IPs	
		AE/SAE recording	At any time of the day
		Concomitant medications	At any time of the day
		End of 24-hour urine sample collection for Day -1	The urine is collected for 24 hours \pm 1 hour. The end of the 24-hour urine collection should be prior to first use of IPs.

Confidentiality Statement

Data and information contained in this document are considered to constitute trade secrets and confidential commercial information, and the legal protections provided to such trade secrets and confidential information are hereby claimed under the provisions of applicable law. No part of this document may be publicly disclosed without the written consent of Philip Morris Products S.A.

Time	Blood Sample	Procedures	Additional Information
Start of Procedure		Day 1	
		Start of 24-hour urine sample collection for Day 1.	The start of 24-hour urine collection of Day 1 should be subsequent to the end of 24-hour urine collection of Day -1.
		Urine sample to be taken from the 24-hour urine of Day -1	Aliquots from 24-hour urine will be collected according to Table A2 . Bio-banking for biomarkers (if additional consent is obtained)
06:30 AM - 09:30 AM		Start of HPT assessment	In both study arms CHTP 1.0 and CC, the HPT SODIM® device has to be used for all smoking events when compatible CCs are smoked
Prior to 11:30 AM		Vital signs (blood pressure, pulse rate, respiratory rate)	At least 5 minutes in supine position
Prior to 11:30 AM		MNWS questionnaire	Has to be done prior to use of IPs
Prior to 11:30 AM		Assessment of cough (VAS)	Has to be done prior to use of IPs
In the evening prior to 9:00 PM (approx. 8:00 PM ± 1 hour)		CO breath test	Has to be done in conjunction with COHb blood sampling
In the evening prior to 9:00 PM (approx. 8:00 PM ± 1 hour)	√	COHb in blood	Has to be done in conjunction with CO breath test
In the evening prior to 9:00 PM (approx. 8:00 PM ± 1 hour)	√	Plasma nicotine and cotinine sample	Cotinine will be measured in the same assay as nicotine. No additional blood samples required
8:00 PM - 11:00 PM		Craving questionnaire (QSU brief)	

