7.2.6 Cough Assessment

Subjects will be asked to assess the respiratory symptom ‘cough’ using a VAS, three Likert scale questions, and one open ended question on a daily basis during the confinement period (on Day -1 to Day 6) prior to 11:30 AM or at 06:29 AM \pm 1 hour on Day 6.

Subjects will be asked if they have experienced a regular need to cough, e.g., whether they have coughed several times in the previous 24 hours prior to assessment. If the answer is ‘yes’, subjects will be asked to complete questionnaire.

The VAS will assess how bothersome cough is to the subject ranging from ‘not bothering me at all’ to ‘extremely bothersome’, and this will be given a numeric value between 0 and 100, measured on a 100 mm scale.

Subjects will also be asked to assess the intensity and frequency of cough and the amount of sputum production on Likert scales as presented in **Table 7**.

Table 7 Cough Assessment Likert Scales

Question	Likert Scale
1 The intensity of cough	1 = very mild 2 = mild 3 = moderate 4 = severe 5 = very severe
2 The frequency of cough	1 = rarely 2 = sometimes 3 = fairly often 4 = often 5 = almost always
3 The amount of sputum production	0 = no sputum

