11.3 Assessment Windows

Smoking of the randomized products should take place within the 06:30 AM and 11:00 PM window.

The assessment windows are shown in **Table 16**.

Table 16: Assessment Windows

Assessment	Nominal Time point(s)	Window
24 h urine sample	Start (All days)	06:30 AM \pm 1 hour
	End on the following day (All days)	06:29 AM \pm 1 hour
CYP1A2 activity in plasma	Start (Days -1 and 5)	6 hours after intake of cup of coffee \pm 15 min
CYP2A6 activity	Day -1 and Day 6	Prior to smoking / product use
CO breath test	Day -2 to Day 5	In the evening prior to 09:00PM (approx 08:00 PM \pm 1 hour)
Assessment of Cough	Day -1 to 5	To be done prior to product use but not later than 11:30 AM
	Day 6	06:29 AM \pm 1 hour
MNWS questionnaire	Day -1 to 5	To be done prior to product use but not later than 11:30 AM
	Day 6	06:29 AM \pm 1 hour
QSU-brief questionnaire	Day -2 to 5	08:00 PM to 11:00 PM
MCEQ questionnaire	Day -2 to 5	08:00 PM to 11:00 PM
Nicotine and cotinine in plasma	Day -2 to Day 5	In the evening prior to 09:00PM (approx 08:00 PM \pm 1 hour)

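### Protocol 7.8.2 waives the time of day for the 24-hour-recall cough form, against the windows in the day tables and SAP Table 16; on Day 1 in the CHTP 1.0 arm the completion time decides which product is recalled

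*Protocol*

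**What the plan says.** On timing, the documents say the following:

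- Protocol 7.8.2, the section specific to this instrument: "Assessment of cough will be conducted irrespective of the time".
- Protocol 7.8, for all questionnaires: "The questionnaires should be done at the same time for each visit".
- Protocol Table 9 (Day -1): before 11:30 AM, and "Has to be done prior to smoking".
- Protocol Tables 10 to 14 (Days 1 to 5): before 11:30 AM, and "Has to be done prior to use of IPs".
- Protocol Table 15 (Day 6): 06:29 AM ± 1 hour.
- SAP Table 16, for Day -1 to Day 5: "To be done prior to product use but not later than 11:30 AM". It repeats the Table 15 window for Day 6.
- SAP 7.2.6: "on a daily basis during the confinement period (on Day -1 to Day 6) prior to 11:30 AM", or the Day 6 window. It does not repeat the pre-use condition.

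On recall, Protocol 7.8.2 says: "On the VAS, subjects will assess how bothersome their cough was during the previous 24 hours". The opening cough question and the Likert scales use the same period.

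On precedence, the introduction to Protocol section 7 says that "adequate time windows will be given for each study procedure and each time point in section 9". No text says that the section 9 tables override 7.8.2.

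**The concern.** Section 7.8.2 permits forms that the day tables and the SAP do not. A form completed in the evening complies with 7.8.2, yet SAP Table 15 would record it as a time deviation for the cough assessment.

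The recall period gives this conflict some substance. Subjects in the CHTP 1.0 arm change product at 06:30 AM on Day 1. A Day 1 form completed before first use looks back on cigarettes only. One completed late that evening looks back mostly or entirely on CHTP 1.0. Both would enter the same Day 1 cell of the by-day cough table, because SAP 12.5.4.5.6 summarises cough on each day by study arm. What is at stake is how the first post-switch cough value reads in the safety tables.

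**Working it through.** The plan gives no figure to reproduce. The check is how the 24-hour recall period overlaps the permitted-use hours on Day 1 in the CHTP 1.0 arm.

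**Inputs**
- Recall period: 24 hours (Protocol 7.8.2).
- Switch to CHTP 1.0: Day 1, 06:30 AM (Protocol 6.3.3).
- Permitted use: 06:30 AM to 11:00 PM, or 16.5 hours a day (Protocol 6.7.1).

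**Formula.** Let t be the completion time in hours after midnight on Day 1, with t between 6.5 and 23. The recall period runs from t − 24 to t. Permitted cigarette use on Day -1 ended at −1 (11:00 PM).
- Cigarette hours recalled = −1 − (t − 24) = 23 − t
- CHTP 1.0 hours recalled = t − 6.5
- The sum is always 16.5, so the CHTP 1.0 share = (t − 6.5)/16.5

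| Form completed on Day 1 | Cigarette hours | CHTP 1.0 hours | CHTP 1.0 share |
|---|---|---|---|
| 06:30 AM, before use | 16.5 | 0 | 0% |
| 11:30 AM | 11.5 | 5.0 | 5.0/16.5 = 30% |
| 2:45 PM | 8.25 | 8.25 | 50% |
| 8:00 PM | 3.0 | 13.5 | 13.5/16.5 = 82% |
| 11:00 PM | 0 | 16.5 | 100% |

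By clock hours since the switch, the last two rows would be 13.5/24 = 56% and 16.5/24 = 69%. Permitted-use hours are the better measure, because overnight hours carry no permitted use of either product. At 11:00 PM no permitted cigarette hours remain in the recall period, so 69% would suggest a mixture that is not there.

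The 11:30 AM row also shows why the omission in SAP 7.2.6 matters. Read alone, that section would accept a form with up to about 30% of its recalled use hours on CHTP 1.0. Table 16 would not.

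**Other days and the other arm.** The CC arm never changes product. In the CHTP 1.0 arm a Day 2 form completed at 06:30 AM reaches back to 06:30 AM on Day 1, so from Day 2 to Day 5 the form recalls CHTP 1.0 whatever the time, if use is compliant. A Day -1 form recalls cigarettes in both arms. One side case remains. Protocol 6.3.4 allows cigarettes on Day 6 once the Day 5 urine collection, spirometry and CYP2A6 sampling are done, so a late Day 6 form could take in some cigarette use. The documents give no clock time for that smoking, so I put no share on it.

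**Day label.** A correctly timed Day 1 form describes Day -1. For the MNWS, the other 24-hour-recall form, SAP 7.2.4 reports data collected on Days -1 to 6 as Days -2 to 5. SAP 7.2.6 and 12.5.4.5.6 state no such shift for cough. Correcting the timing alone would therefore leave a form about cigarettes labelled as Day 1 of CHTP 1.0 use.

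**The case against.** The strongest reply is that the plan already handles this. Section 7 sends the reader to section 9 for windows. Section 9 allows any time of day only where no start time is given, and the cough form has a time entry in every table from Day -1 to Day 6. SAP Table 16 follows those tables. A form completed before use satisfies both 7.8.2 and the tables, so a site working from the day schedules would never meet the conflict. Late forms are already a named deviation category, classed as minor, and deviations are listed and summarised. Cough is descriptive, and no test, alpha or power depends on it. Nearly all of this stands, and it limits the weight of the point. It does not remove the contradiction: 7.8.2 is the instruction specific to this form, it expressly waives timing, and nothing ranks it below the tables.

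A reader might infer three stronger things that the documents do not support:

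- That free timing changes the recalled product throughout the study. During the Exposure Period it does so only on Day 1, and only in the CHTP 1.0 arm.
- That timing would differ by arm because the study is open-label. Nothing says that subjects choose when to complete the form, and the CC arm has no product mix to differ.
- That evening completion was planned. No table schedules cough at 8:00 PM or 11:00 PM; those rows show only what 7.8.2 would permit.

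**Conclusion.** The point holds as a contradiction within the current protocol, and between it and the SAP, with a small and well-defined consequence. On Day 1 in the CHTP 1.0 arm, free timing lets the form describe anything from cigarettes only (0% of recalled use hours on CHTP 1.0) to CHTP 1.0 only (100%), and a form after 2:45 PM describes mostly the new product. The figures assume exclusive use of the assigned product, use available from 06:30 AM, and permitted hours as a stand-in for actual use. If first use is later, the CHTP 1.0 share at a given time is lower.

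The effect stops at the descriptive cough summaries. How many forms would be affected is unknown, and would be none at a site that follows section 9. The missing day label matters whichever timing rule is followed, because it affects correctly timed forms as well.

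**What to change.** 1. In Protocol 7.8.2, delete the sentence that waives timing and refer to the section 9 tables, whose windows SAP Table 16 repeats.
2. In SAP 7.2.6, add the pre-use condition so that it agrees with Table 16.
3. In the by-day cough table (15.2.6.21.1), flag forms completed after first product use that day. Do not exclude them: they are subject-reported safety data, and a late form is still valid for the period it recalls.
4. State in SAP 7.2.6 and 12.5.4.5.6 which exposure day each cough form represents, using the same one-day shift as the MNWS, so that a pre-use Day 1 form is reported as Day -1.

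No procedure or visit is added. The protocol change is one sentence, but Protocol 1.1 requires every amendment to go to the ethics committee. The SAP changes are a few lines, a flag and a relabelled day. SAP section 3 allows amendments until database lock, so items 2 to 4 remain possible even if collection has finished.
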